2.3.1.2 Primary outcome - diet

As dietary change evokes a spectrum of changes, the study will use four primary outcomes for diet.²⁰

¹⁸ Biswas A, Oh PI, Faulkner GE, Bonsignore A, Pakosh MT, Alter DA. The energy expenditure benefits of reallocating sedentary time with physical activity: a systematic review and meta-analysis. Journal of Public Health. 2018 Jun 1;40(2):295-303.

¹⁹ Saint-Maurice, P. F., Troiano, R. P., Bassett, D. R., Graubard, B. I., Carlson, S. A., Shiroma, E. J., ... Matthews, C. E. (2020). Association of Daily Step Count and Step Intensity With Mortality Among US Adults. *JAMA*, *323*(12), 1151–1160. doi: 10.1001/JAMA.2020.1382

²⁰ In previous versions of the evaluation protocol, calorie intake had been selected as the primary outcome for diet. The DOPA/OHID expressed concerns around use of kcal as the primary outcome measure for diet, in particular around i) underreporting, and ii) the fact that the pilot is not a weight loss programme and so there was the concern of not being able to detect a change in kcals even if the pilot did improve participants' diet. Following further conversations with the DOPA/OHID, BIT and DHSC agreed on the list of primary outcomes included in the current evaluation protocol, that reflect behaviours that are directly incentivised by the programme.

These include:

- Fruit and vegetables (g/day)
- Fibre (g/day)
- Saturated fat (% daily food energy²¹ intake)
- Free sugars (% daily food energy intake)

Evidence suggests that people typically consume insufficient amounts of fruit and vegetables and fibre whilst overconsuming saturated fat and free sugars.²² (Also see Appendix C for an overview of the recommended dietary intake **according to UK** dietary recommendations).

Tackling the primary outcomes above, might benefit health:

- Fruit and vegetable consumption: The health benefits of increased fruit and vegetable consumption include reduced risk of cardiovascular disease, cancer, and all-cause mortality.^{23 24} A recent meta-analysis also provided moderate certainty evidence that consuming fresh fruit promotes weight maintenance or modest weight loss over periods of 3–24 weeks.²⁵ This is in line with other evidence suggesting increased fruit and vegetable consumption can support maintenance of a healthy weight.^{26 27}
- **Fibre consumption:** Consumption of whole-grain and dietary fibre has been associated with lower mortality, and lower risk of CVD, obesity, and diabetes.²⁸

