2.4.2.4 Minimum detectable effect size given the sample size at analysis stage

With the sample size at the final data collection point (i.e. post-attrition, n = 4,200), we present the minimum effects we are powered (at 80% level) to detect for six primary outcomes among the trial participants in Table 7, which also provides corresponding benchmarks to interpret those effect sizes.

Table 7. Minimum detectable effect size for primary outcomes given a post-attrition sample size of 4,200

Prima	ry outcomes	MDES	MDES as % of min. (or max.) recommended intake
PA	Daily MVPA (min/day)	2.4 min/day	~ 10% (150 min/week, according to the UK CMO's Physical Activity Guidelines)
	Daily steps	371 steps/day	~ 4% (8,000 steps/day, according to the UK CMO's Physical Activity Guidelines)
Diet	Fruit and vegetables (g/day)	18.7 g/day	~ 5% (~ a quarter of a F&V portion)
	Fibre (g/day)	0.74 g/day	~ 2.5% (~ a third of an apple)
	Free sugars (% food energy)	0.63%	~ 13% of the upper limit of % food energy intake (≤5% food energy)
	Saturated Fat (% food energy)	0.31%	~ 2.8% of the upper limit of % food energy intake (≤11% food energy)

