- *missing. baseline*_{*ijd*} is a dummy variable that equals 1 if *baseline*_{*ijd*} is missing and 0 otherwise and will capture whether MVPA is systematically different for individuals who are missing baseline data for the same day;
- X_{ij} are individual level (including age, sex, ethnicity, education, BMI at baseline, and brand of wearable) and family level covariates we will take missing values for these covariates as separate categories rather than imputing;
- δ_{c_j} are the cluster (i.e. household) level random effects, which have mean zero and follow a normal distribution;
- For each family *j*, $\delta_{p_{ij}}$ are the individual (person) level random effects, which have mean zero within each household and follow a normal distribution;
- u_{ijd} is an idiosyncratic error term. We will use a compound symmetry covariance structure (default for a model with random intercepts).

The primary outcomes for diet are:

- Fruit and vegetables (g/day);
- Fibre (g/day);
- Free sugars (% daily food energy);
- Saturated fat (% daily food energy);

as self-reported in Intake24 recalls at the 5-month follow-up point. We will use a similar model to analyse this outcome, as shown below:

(2)
$$y_{ij} = \alpha + \beta Treatment_{j} + \gamma_{D} weekday_{ij} + \gamma_{W} week_{ij} + \gamma_{N} num. admin_{ij} + \dots \gamma_{B} baseline_{ij} + \gamma_{A} weekday. baseline_{ij} + \gamma_{X} X_{ij} + \delta_{Cj} + u_{ij}$$

$$\delta_{cj} \sim N(0, \sigma_c^2)$$
 for all j; $u_{ij} \sim N(0, \sigma_u^2)$ for all i, j

where:

- y_{ij} is person *i*'s energy intake according to Intake24 surveys at 5 months. If the person took two surveys, we average their reports;
- weekday_{ij} is the proportion of administrations at 5 months that occurred on a weekday (rather than on the weekend). For example, if an individual had one administration on Monday and one on Saturday, weekday. ind_{ij} equals 0.5. This is intended to account for the difference in dietary patterns between

weekdays and the weekend;

- *num. admin*_{ij} is the number of administrations at 5 months (1 or 2);
- baseline_{ij} is calculated in an analogous way to y_{ij}, but for the administration(s) at baseline;
- *weekday.baseline*_{ij} is calculated in an analogous way to *weekday*_{ij}, but for the administration(s) at the baseline;

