- All other variables are defined in an analogous way to equation (1). Note that we do not use person-level random effects because there is only one observation per person in the sample.

We are using two primary outcomes, which raises the probability of a false discovery being made on at least one of them. To control for the false discovery rate over primary outcomes, we perform the Benjamini-Hochberg step-up procedure.

2.6.3.6 Analytical strategy for the secondary analysis: Broader effect of offering financial incentive on holistic constructs

The impact of offering incentives (compared to not offering any incentives) on secondary outcomes at the 5 months mark will be assessed using similar methods as the ones for the primary analysis.

2.6.3.7 Analytical strategy for the secondary analysis: Short- and medium-term impacts on primary outcomes

We will estimate the same models as at 5 months (i.e. as in section 2.6.3.5) for the primary outcomes using outcome data from 1 month and 3 months to analyse the average impact of incentives over those shorter time periods. As described above, the three-month outcomes will be the focus for the study should attrition at five months prohibit meaningful analysis at five months.

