Adults per household	Number of households	% of total (102,177 households)		
1	39,777	39%		
2	41,784	41%		
3+ *	20,616	20%		
* set to 3 for simplicity in estimations as Census 2011 data does not provide further granularity				

* set to 3 for simplicity in estimations as Census 2011 data does not provide further granularity

Adjusting for multiple comparisons

For the primary outcomes, we will adjust for multiple comparisons using the Benjamini-Hochberg procedure within the physical activity outcomes (2 comparisons) and dietary outcomes (4 comparisons) separately. For the exploratory outcomes and questions, we will adjust for multiple comparisons separately within each research question and separately for physical activity and dietary outcomes. For example, when examining effects after 1 month on the primary outcomes, we will perform 2 comparisons for the physical activity outcomes and 4 for the dietary outcomes. We will do the same for the analysis at 3 months.

Baseline measures and other covariates

We assume that the inclusion of covariates such as baseline calorie intake, baseline MVPA min/day, socio-demographic information, and anthropometric information will reduce variance in the outcome measures, and therefore increase power. Based on prior research, the pre-post correlation in the calorie intake measure using Intake24 is expected to be ~0.5; for the measure of MPVA min/day this is expected to be ~0.8.⁹² Therefore, we conservatively assume that a correlation coefficient of at least 0.5 is realistic in this trial.⁹³

⁹² https://www.ncbi.nlm.nih.gov/pmc/articles/PMC6722486/;

https://journals.humankinetics.com/view/journals/jpah/8/5/article-p668.xml

⁹³ Note that our estimates are additionally conservative because we do not explicitly factor in multiple measurements per participant during both baseline and outcome timepoints (e.g. participants will be asked to complete two Intake24 measurements during baseline, and will be asked to wear the wearable device every day). We have chosen to not factor this in due to the uncertainty around compliance with the Intake24 and daily wearing of the wearable devices.

Appendix C - Recommended dietary intake according to the Recommended dietary intake according to the Government Dietary Recommendations

Outcome	Current intake	Desired change
Carbohydrates	212 g/day	Increase
Free sugars	51 g/day	Reduce
Total Fat	69 g/day	Met
Saturated fat	25 g/day	Reduce
Fibre	18 g/day	Increase

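### Section 2.6.3.5 lists six primary outcomes but keeps two remnants of an earlier version: energy intake as the diet response, and Benjamini-Hochberg over two outcomes

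*Protocol*

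**What the plan says.** **Outcome set.** Section 2.3.1.2 says "the study will use four primary outcomes for diet", and section 2.3.1.1 names two for activity. Section 2.4.2.4 gives the minimum effects "we are powered (at 80% level) to detect for six primary outcomes among the trial participants in Table 7". Tables 3 and 11 and section 2.3.2.2 place energy intake among the secondary outcomes. A footnote to section 2.3.1.2 gives the history: "In previous versions of the evaluation protocol, calorie intake had been selected as the primary outcome for diet".

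**Primary analysis, section 2.6.3.5.** The section names MVPA and steps as the activity outcomes and lists the four diet outcomes directly above equation (2). In the definitions under that equation, however, the response is the person's "energy intake according to Intake24 surveys at 5 months", and the baseline term is calculated analogously to the response. The section ends with "We are using two primary outcomes, which raises the probability of a false discovery being made on at least one of them", followed by "To control for the false discovery rate over primary outcomes, we perform the Benjamini-Hochberg step-up procedure".

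**Multiplicity elsewhere.** Appendix B applies Benjamini-Hochberg "within the physical activity outcomes (2 comparisons) and dietary outcomes (4 comparisons) separately". Table 5 uses the same counts, 2 and 4, with Bonferroni for the power calculation, and its footnote says Benjamini-Hochberg will replace Bonferroni at analysis.

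**The concern.** Section 2.6.3.5 is where the primary model is written down. Later sections refer back to it for the 1- and 3-month effects, the incentive levels and the subgroups. Two things in it do not match the rest of the protocol.

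- **Diet response.** Taken literally, equation (2) estimates the effect on energy intake and adjusts for baseline energy intake. None of the four stated diet outcomes would be analysed.
- **Multiplicity family.** A procedure over two outcomes cannot hold the six just listed, and a single procedure over the primary outcomes is not the same as two separate ones. Whether a diet result is declared can depend on which wording is followed. That choice should not be open once p-values are known.

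**Working it through.** **1. The passages side by side.** The footnote in 2.3.1.2 says calorie intake was formerly the diet primary outcome. In 2.6.3.5, equation (1) describes its response only as daily MVPA minutes, equation (2) only as energy intake, and the closing count is two. One activity response plus one diet response makes two, so these phrases fit the earlier outcome set. That is an inference, but the conflict with the six outcomes listed in the same section is plain without it.

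**2. Which family structure the power calculation uses.** Inputs:

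- 2,100 control and 2,100 pooled incentive users, 80% power (section 2.4.1).
- ICC 0.3 and baseline correlation 0.5 (section 2.4.2.2).
- Households 39% / 41% / 20% with 1 / 2 / 3 adults, and the SDs (Table 5).
- Two-sided 0.05: assumed, because the protocol gives no level.

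Mean household size = 0.39 + 2(0.41) + 3(0.20) = 1.81. This gives 4,200/1.81 = 2,320 households, in line with the plan's figure of about 2,300. Design effect = 1 + (1.81 − 1)(0.3) = 1.243.

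MDES = (z for α/2 + 0.842) × SD × √[(2/2100) × 1.243 × (1 − 0.5²)], where the square root is about 0.0298 and α = 0.05 divided by the family size.

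| Outcome | SD | Stated MDES | Divisor 2 | Divisor 4 | Divisor 6 |
|---|---|---|---|---|---|
| MVPA (min/day) | 26 | 2.4 | **2.39** | 2.59 | 2.70 |
| Steps/day | 4,096 | 371 | **376** | 408 | 425 |
| Fruit and vegetables (g/day) | 190 | 18.7 | 17.5 | **18.9** | 19.7 |
| Fibre (g/day) | 7.5 | 0.74 | 0.689 | **0.746** | 0.778 |
| Free sugars (%) | 6.3 | 0.63 | 0.579 | **0.627** | 0.653 |
| Saturated fat (%) | 3.2 | 0.31 | 0.294 | **0.318** | 0.332 |

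With divisor 2 for activity and 4 for diet (bold), every value is within 3% of the one stated. Divisor 2 for diet gives values 5% to 8% too low. Divisor 6 throughout gives values 4% to 15% too high.

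A second check does not depend on the ICC, the baseline correlation or the household sizes, provided they are common to both domains. In SD units the stated MDES average (0.0923 + 0.0906)/2 = 0.0915 for activity and (0.0984 + 0.0987 + 0.1000 + 0.0969)/4 = 0.0985 for diet, a ratio of 1.077. The 2 + 4 split predicts (2.498 + 0.842)/(2.241 + 0.842) = 1.083. A common divisor predicts 1.00.

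**3. Effect on a declared result.** Benjamini-Hochberg compares the i-th smallest of m p-values with 0.05 × i/m.

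- m = 2: 0.025, 0.05.
- m = 4: 0.0125, 0.025, 0.0375, 0.05.

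Suppose one diet outcome has p = 0.02 and every other p-value exceeds 0.05. It is declared with m = 2 (0.02 ≤ 0.025) and not with m = 4 (0.02 > 0.0125).

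**4. What separate families control.** If each domain's procedure holds its own 5% and the domains are independent, the chance of at least one false declaration when no effect exists is 1 − 0.95² = 9.75%; without independence it is bounded by 10%. This follows from the per-domain design, which is a legitimate choice. It does not measure the wording error. It shows only that control over all six primary outcomes should not be claimed.

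**The case against.** The strongest reply is that the intent is recoverable. Section 2.6.3.5 lists all six outcomes correctly, Appendix B gives a usable rule, Table 5 agrees with it, and section 2.4.1 sends the reader to Appendix B for multiplicity. The count of two might also mean two outcome types. Most of this stands: a careful analyst would probably apply 2 + 4. But reading two as two types does not repair the response in equation (2), nor the single procedure over the primary outcomes.

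It is also fair that the smallest-p threshold is not the whole rule. The procedure is step-up, and if every p-value in a family is at or below 0.05, all are declared whatever the family size. The family matters in mixed results such as the example above.

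A reader might infer that an energy-intake baseline would fail to deliver the 0.5 correlation assumed for power. The documents do not support that. The baseline is defined analogously to the response, so the two are always the same variable, and Appendix B expects about 0.5 for calorie intake itself. The Appendix B phrase "the inclusion of covariates such as baseline calorie intake" is an example in a paragraph on power assumptions and does not specify a model.

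**Conclusion.** The point holds as an internal contradiction in current text. Two phrases in 2.6.3.5 are wrong as written: the diet response (with its baseline) and the multiplicity sentence. Followed literally, they lead to the wrong diet analysis and to a smallest-p threshold of 0.025 where Appendix B implies 0.0125 for diet. Both thresholds rest on an assumed two-sided 0.05.

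A reader might conclude that the section as a whole still specifies the old outcome set, or that the trial is mis-sized. Neither follows. The six outcomes are listed correctly in the same section, and the stated MDES already rest on families of 2 and 4, so 4,200 users and the MDES stand. Nor does the plan's power calculation use a single family of six, so no loss of power should be inferred from one.

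**What to change.** In section 2.6.3.5:

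1. Define the response in equation (2) as each of the four diet outcomes in turn, with the baseline of that same outcome.
2. Replace the closing count of two by six primary outcomes, with Benjamini-Hochberg applied separately within activity (2) and within diet (4), as in Appendix B.
3. State the false discovery rate level used, since neither Appendix B nor Table 5 gives one.
4. Say that the rate is controlled within each domain and not over all six outcomes.

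The cost is protocol wording only. Sample size, MDES and data collection are unaffected.

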2.6.3.8 Analytical strategy for the secondary analysis: Impact of different incentive levels

The impact of each incentive level on the primary outcomes will be assessed using the same approach as the one for the primary analysis but we will categorise the treatment indicator differently. In these regressions, *Treatment*, will be a series of

three dummy variables, each of them taking value 0 for households (or users for the individual level randomisation) allocated to the control group, and 1 for households (users) allocated to the specific treatment group for low, medium or high levels of incentives.

This approach will allow us to statistically compare the effect of each incentive with the control group.

2.6.3.9 Analytical strategy for the exploratory analysis: subgroup analysis

To help us understand how the intervention might work differently for different subgroups, we will repeat the same analysis as specified in the primary analysis above for primary outcomes, for each of the following subgroups separately:

Subgroups of interest	Cut-off criteria	Expected proportion of the sample
People who live in the most deprived areas	Participants will be categorised as living in the most deprived areas if their post code corresponds to Index of Multiple Deprivation (IMD) ≤ 2 (top 20% most deprived)	51.3% (source: Wolverhampton deprivation status)
Ethnicity	5 GSS macro groups [White / Mixed or multiple ethnic groups / Asian or Asian British / Black or African or Caribbean or Black British / Other ethnic group]	White: 68%; Asian: 18%; Black: 7%; Mixed: 5% Others: 2% (source: Wolverhampton's census statistics)
Sex	Male; female; prefer not to say	~ 50% males (source: Wolverhampton's census statistics)
Age	Age ≤ median age of the sample; Age > median age of the sample	~ 50% vs. 50%
Baseline diet	Self-reported daily consumption of fruit and veggie ≥ 3 portions self-reported daily consumption of fruit and veggie < 3 portions	~ 62% (≥ 3 portions) vs. 38% (< 3 portions) ⁶⁰

Table 12. Subgroups

⁶⁰ According to the Health Survey for England, on average, adults consume 3.7 portions per day, and given that the standard deviation is 2.4 portions per day, 3 portions/day is about 0.3 SD below the average, corresponding to 38% of the population assuming the distribution of fruit and vegetable consumption is normal.

active) MVPA < 30 mins / week (inactive)	~ 73% (active) vs. 27% (inactive), according to the Sport England Active Lives Survey
---------------------------------------------	-------------------------------------------------------------------------------------------------------

2.6.3.10 Analytical strategy for the exploratory analysis: Motivation to change and unintended consequences

The impact of offering incentives (compared to not offering any incentives) on exploratory outcomes at the 5 months mark will be assessed using similar methods as the ones for the primary analysis. We will not impute values at baseline or at 5 months. If there are missing values for an exploratory outcome at baseline, we will add an indicator variable for missingness to the set of covariates so that all individuals with non-missing values for the outcome at 5 months can be included.

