2.1 Objectives and hypotheses

The primary objective of the impact evaluation study is to assess the effectiveness of the financial incentive scheme at

• increasing moderate-vigorous physical activity (MVPA minutes/day and steps/day) among adults recruited from the general public in Wolverhampton.

and

 improving the healthfulness of the diet (fruit and vegetables in g/d, fibre in g/d, free sugars in % of food energy/day, and saturated fat in % of food energy/day) among adults recruited from the general public in Wolverhampton.

BIT's impact evaluation will be designed to test the hypothesis that financial incentive schemes significantly increase physical activity (PA) levels (throughout, this is defined through our two primary outcomes for physical activity) and improve the healthfulness of recipients' dietary intake (throughout, this is defined through our four primary outcomes for diet), by comparing the behaviour of users allocated to a control group (no financial incentives offered) to the behaviour of users allocated to the pooled treatment groups (low, medium or high level of financial incentive offered).

The secondary research questions include:

- **Broader effects on PA and diet:** Does offering financial incentives significantly affect participants' energy expenditure, energy intake, their score on a healthy eating score based on consumption of key food groups, macro-and micronutrients, and weight) five months after randomisation?
- **Shorter-term effects:** Does offering financial incentives effectively improve participants' dietary intake and PA in the shorter term (one and three months after randomisation), comparing the behaviour of users allocated to a control group (no financial incentives offered) to the behaviour of users allocated to the pooled treatment groups (low, medium or high level of incentive offered)?
- **Optimal incentive value:** Do different levels of financial incentives achieve different effect sizes on participants' dietary intake and PA level five months after randomisation, comparing the behaviour of users allocated to a control group (no financial incentives offered) to the behaviour of users allocated to

each treatment group (low, medium and high level of incentive offered)?

The exploratory research questions include:

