- **Subgroup analyses:** Does the incentive scheme also work among specific population subgroups five months after randomisation in terms of improving dietary intake and PA (focusing on primary outcomes), comparing the behaviour of users allocated to a control group (no financial incentives offered) to the behaviour of users allocated to the pooled treatment groups (low, medium or high level of incentive offered)?
- Longer-term effects on motivation to change: Does offering financial incentives effectively increase participants' motivation to improve dietary intake and to increase PA level five months after randomisation, comparing the motivation level of users allocated to a control group (no financial incentives offered) to that of users allocated to the pooled treatment groups (low, medium or high level of incentive offered)?
- Unintended consequences: Does the incentive scheme have any significant impact on participants' sleep or mental health five months after randomisation, comparing the behaviour of users allocated to a control group (no financial incentives offered) to the behaviour of users allocated to the pooled treatment groups (low, medium or high level of incentive offered)?

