2.4 Sample size and minimum detectable size

2.4.1 Summary

The trial will adopt **a household-level randomisation**, with a target sample size of **around 4,200 participants** (2,100 in the control arm, 700 per intervention arm) at the final data collection point (**5 months after the randomisation**) to be powered to detect effect sizes deemed substantive from previous literature (see Section 2.4.2.2 Table 5). We expect users to come from ~2,300 households based on the demographic profile of Wolverhampton LA (see Appendix B).

To achieve a post-attrition sample of 4,200 participants, HUL expects to recruit a sample of around **25,800 participants** at the beginning of the baseline stage, given the attrition rate at various trial stages estimated by HUL (see Section 2.4.2.3 Table 6).

BIT has conducted power calculations for the primary research question "Does the incentive scheme improve physical activity (PA) and diet at the five month mark?". The power calculations focus on the primary outcomes. The primary analysis pools all the treatment arms together and assesses their overall difference against the control.

Given the post-attrition sample size of 4,200 participants, the minimum effect sizes we are powered (at 80% level) to detect at the 5-month's mark in the primary analysis are:

Physical activity primary outcomes:

- Daily MVPA (min/day): 2.4 min/day
- Daily steps: 371 steps/day

Dietary primary outcomes:

- Fruit and vegetables (g/day): 18.7 g/day
- Fibre (g/day): 0.74 g/day
- Free sugars (% food energy): 0.63%
- Saturated Fat (% food energy): 0.31%

The following subsections provide details on the key assumptions and decisions made concerning the power calculation. First, we provide the minimum required sample size at the analysis stage (post-attrition) given the target effect sizes for the primary outcomes (see Table 5). Then, we show the minimum required sample size at the recruitment stage (pre-attrition) given the predicted attrition rate at various stages (see Table 6) based on HUL's estimations. Last, we calculate the minimum detectable effect size for primary outcomes (see Table 7) based on the target sample size confirmed as feasible for this project by HUL and DHSC.

For further information on specific assumptions behind household-level randomisation, multiple-comparisons-adjustment, inclusion of covariates, and allocation ratio among trial arms, please see Appendix B.

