Number of overall users required for smaller dietary outcome target MDES at the 5m mark analysis stage	4,200 (2,100 in control; 700 per intervention arm)			

⁴⁶ The Benjamini-Hochberg false discovery adjustment will be applied during analysis of primary outcomes, but as it is not possible to apply this before having the data, the more conservative Bonferroni adjustment provides an upper bound on power here.

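### The protocol asks whether incentive levels differ in effect and how subgroups might respond differently, but pre-specifies no level contrast, trend or interaction that would test a difference

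*Protocol*

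**What the plan says.** **Incentive levels (secondary).** Protocol section 2.1, under the heading on the optimal incentive value, asks: "Do different levels of financial incentives achieve different effect sizes". The same sentence goes on to name its comparison as control against each treatment group. Section 2.6.3.8 replaces the single treatment indicator with three dummies in one model and concludes: "This approach will allow us to statistically compare the effect of each incentive with the control group".

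**Subgroups (exploratory).** Section 2.6.3.9 gives its purpose as "To help us understand how the intervention might work differently for different subgroups". Its method is "we will repeat the same analysis as specified in the primary analysis above for primary outcomes, for each of the following subgroups separately". The formal research question in section 2.1 is narrower: "Does the incentive scheme also work among specific population subgroups five months after randomisation".

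**Multiplicity.** Appendix B adjusts within each research question, separately for activity and diet. That rule governs the separate tests; it does not compare them with each other.

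The protocol contains no level-against-level contrast, joint test of equal effects, trend across levels or treatment-by-subgroup interaction.

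**The concern.** Whether levels achieve different effect sizes, and whether the scheme works differently across subgroups, are questions about differences between effects. A set of tests against control does not answer them. One level can reach significance and another miss it when both have the same true effect, simply because each comparison has moderate power.

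The Introduction says the pilot is meant to guide decisions on scaling the scheme, and the incentive value bears directly on its cost. If the high level were significant and the low level not, the report would hold no pre-specified estimate, with its uncertainty, of the difference between them. The same applies to a subgroup pattern. It applies most to ethnicity, where the expected shares run from 68% down to 2% and significance would largely follow sample size.

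**Working it through.** **Inputs.**
- From the protocol: 2,100 control and 700 per incentive arm at five months; 80% power; Bonferroni over 2 activity and 4 diet outcomes (Table 5); household ICC 0.3 and baseline correlation 0.5 (section 2.4.2.2); households of 1, 2 and 3 adults at 39%, 41% and 20%; SD 190 g/day for fruit and vegetables and 26 min/day for MVPA.
- Assumed, because the protocol does not state it: two-sided 5% alpha, so 0.025 per activity outcome and 0.0125 per diet outcome after Bonferroni. The analysis will use Benjamini-Hochberg, whose threshold lies between the Bonferroni and unadjusted values, so results are shown for that range.

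**Reproducing the plan's figures.**
- Mean household size = 0.39×1 + 0.41×2 + 0.20×3 = 1.81
- Design effect = 1 + (1.81 − 1)×0.3 = 1.243
- Residual SD factor = √((1 − 0.5²)×1.243) = 0.9655
- Fruit and vegetables: (2.498 + 0.842)×190×0.9655×√(2/2100) = 18.9 g/day (stated 18.7)
- MVPA: (2.241 + 0.842)×26×0.9655×√(2/2100) = 2.39 min/day (stated 2.4)

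All six stated values are reproduced within 3%.

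**Power of each separate test.**
- Half-sample subgroup (1,050 v 1,050): SE = 0.9655×√(2/1050) = 0.0421 SD
- One level against control (700 v 2,100): SE = 0.9655×√(1/700 + 1/2100) = 0.0421 SD, the same value
- Power ≈ Φ(effect/SE − z)

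**Disagreement when the true effect is uniform.** For two equal subgroups with power p each, the chance that exactly one is significant is 2p(1 − p). This treats them as independent, which is approximate because one household can span two subgroups. For three levels, the chance that one or two of three are significant was simulated with correlation 0.25 from the shared control.

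| True effect | Alpha | Power each | Two halves disagree | Three levels mixed |
|---|---|---|---|---|
| Diet MDES, 18.7/190 = 0.098 SD | 0.05 | 65% | 46% | 58% |
| Same | 0.0125 | 44% | 49% | 62% |
| MVPA MDES, 2.4/26 = 0.092 SD | 0.05 | 59% | 48% | 61% |
| Same | 0.025 | 48% | 50% | 63% |
| Diet target, 0.11 SD | 0.05 | 74% | 38% | 49% |
| Same | 0.0125 | 54% | 50% | 62-63% |
| Activity target, 0.2 SD | 0.05 | 99.7% | 0.5% | 0.8% |
| Same | 0.025 | 99.4% | 1.2% | 1.8% |
| Same | 0.0125 | 98.8% | 2.4% | 3.5% |

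Setting the diet effect at exactly the value that gives 80% power (3.339 standard errors in the full sample) yields 45% and 57% at alpha 0.05. This sets the lower ends of the 45-50% and 57-63% ranges.

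The five ethnic groups give a mixed result in 68-89% of trials at the diet MDES and still 98-99% at 0.2 SD. With no effect at all and alpha 0.05, two halves disagree in 9.5% of trials and three levels in 14%.

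**Direct tests.** A single contrast or interaction test at 5% would call a uniform effect a difference 5% of the time. What such tests can detect at 80% power:
- Level against level (700 v 700): 2.802×0.9655×√(2/700) = 0.145 SD at alpha 0.05; 3.339×0.9655×√(2/700) = 0.172 SD at 0.0125. For fruit and vegetables that is 27 to 33 g/day.
- 50/50 interaction: 2.802×0.9655×√(4/1050) = 0.167 SD (32 g/day) at alpha 0.05.

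A difference as large as the main diet MDES (0.098 SD) would have about 48% power between two levels and 38% in a 50/50 interaction.

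**The case against.** **The analyses match the questions as formally worded.** The subgroup question in section 2.1 asks whether the scheme also works within subgroups, and separate fits address that. The level question names control as its comparator, and section 2.6.3.8 follows it. This stands in part. It does not remove the mismatch: the level question still asks about different effect sizes, and section 2.6.3.9 still gives differential effects as its purpose.

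**Differences between levels are available.** The three dummies sit in one model, so contrasts can be computed from it. This stands. A reader might infer that the design cannot inform a comparison of levels; that is too strong. The gap is that no contrast is pre-specified.

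**Nothing says differences will be claimed from significance labels.** Results are to be reported as absolute differences, and the subgroup work is exploratory, with two of its six subgroups subject to contract. This stands and lowers the stakes, more for subgroups than for the secondary level question.

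**The size is conditional.** A reader might infer that a uniform effect would usually look like a difference whatever its size. The figures do not support that: at 0.2 SD, two equal halves or three levels disagree in under about 4% of trials, although ethnicity remains mixed.

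**The direct tests are weak.** True: their detectable differences exceed the whole 0.11 SD diet target. That argues for reporting intervals, not for leaving the comparison out. Nor is the lack of a detectable difference between levels a fault in itself, since section 2.4.1 confines power to the primary question.

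**Conclusion.** The point holds in this form: the protocol poses a secondary question about differences between incentive levels and an exploratory aim about differences between subgroups, and pre-specifies only tests that do not assess a difference. At the stated diet or activity minimum detectable effect, with a uniform true effect, two equal subgroups disagree in significance in about 45-50% of trials and the three levels give a mixed result in about 57-63%. At a 0.2 SD activity effect both are below about 4%.

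These figures assume a two-sided alpha between 0.0125 and 0.05, 4,200 participants analysed, the plan's ICC of 0.3 and baseline correlation of 0.5, a design effect based on mean household size, and independence between subgroups. The primary analysis is not affected. The change should be made; it matters more for the levels than for the subgroups.

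**What to change.** **Section 2.6.3.8.** From the existing three-dummy model, pre-specify the high-low, medium-low and high-medium contrasts with confidence intervals, plus one linear trend across levels (or a joint test of equal effects). Treat these as one family per outcome category under the Appendix B multiplicity rule.

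**Section 2.6.3.9.** For each outcome, fit one full-sample model with a treatment-by-subgroup interaction. Base any claim that subgroups differ on the interaction estimate and its confidence interval, and report within-subgroup effects as descriptive.

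**Interpretation.** State that these comparisons have limited power, with a level-against-level detectable difference of about 0.14-0.17 SD against a diet target of 0.11 SD, and more if the adjusted threshold is stricter than 0.0125. Report the intervals, and do not read a non-significant difference as equality.

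**Cost.** Wording, a few contrasts from a model already being fitted, and one set of interaction terms per subgroup factor. No new data, participants or design change.
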